Although PA is important for cancer survivorship, the majority of cancer survivors do not meet recommended PA guidelines. Currently, it is recommended that cancer survivors engage in ≥ 150 min/week of moderate-intensity PA⁹. However, it is estimated that up to 47% of cancer survivors fail to meet this guideline as assessed via self-report PA measures¹³⁻¹⁷. This percentage is likely even higher, given that prior studies in cancer and non-cancer populations have shown three- to six-fold reductions in PA estimates when assessed via accelerometers (a wearable device to objectively-assess PA), versus self-report PA¹⁸⁻²⁰.

Despite strong evidence that regular PA has numerous health benefits for cancer survivors, *how to* promote sustained changes in PA among inactive cancer survivors is not well understood²¹. This is largely because the majority of high-quality randomized trials examining the effect of exercise training on health parameters for those living with cancer or beyond have utilized intense exercise training regimens, where supervised exercise is performed several times per week for multiple weeks at a laboratory or research center. While these studies are important and a necessary first step towards understanding the role of exercise in cancer prevention and survivorship, these strict exercise training protocols are unrealistic to implement on a large scale and have limited dissemination potential; thus it is necessary that effective and translatable interventions for increasing PA among cancer survivors are developed and implemented. In addition, there is a lack of evidence to inform whether these benefits extend to those survivors on extended treatments.

Automated, Internet-based PA programs allow for wide-scale dissemination at a relatively low cost. Pew Research data show that >90% of Americans use the Internet²², making it an ideal medium for delivering behaviorally-based PA interventions, as it can reduce provider costs and reach larger numbers of individuals. Further, the cost of delivering an automated Internet program is low, and there is no added cost for enrolling additional participants, which is important from a translation perspective into healthcare settings.

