Although eHealth interventions are widely used to promote PA and other lifestyle behaviors in 'non-clinical' settings or for patients with specific chronic diseases (e.g., CVD, diabetes), application of these technologies to promote PA in cancer survivors lags behind and is a relatively new concept²³. A recent systematic review²³ identified only five Internet interventions targeting increases in PA among cancer survivors. Of those, only three were randomized trials with a control group, four used a self-report measure of PA, and four were <12 weeks in duration. While overall, these studies showed preliminary support that web-based interventions can increase PA among cancer survivors, additional research is clearly needed.

The proposed study addresses significant limitations in this area of research and examines the feasibility, acceptability, and preliminary efficacy of a 12-week, fully-automated Internet program for increasing PA among cancer survivors, by including those off all cancer treatment and those stable on continuous anticancer therapy - thereby adding to the scant body of literature examining the effect of Internet interventions in this population. It further extends the PA and cancer literature by using rigorous methodology (accelerometers) for assessing changes in PA, not limiting the inclusion criteria to one particular cancer type

(e.g., breast cancer only), utilizing a randomized design which allows for comparison to a usual care control condition, testing an Internet program that is driven by behavioral theory, incorporating the most effective behavioral intervention components (see Innovation), and addressing the need for longer-term interventions (>6 weeks) which also assess the maintenance of PA post-treatment (i.e., 24-wk assessment). Findings from this study have potential to lead to a larger trial with clinical implications for increasing PA in cancer survivors.

STUDY AIMS

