- **Primary aim 1:** Evaluate the feasibility, acceptability, and engagement with the EEP. Feasibility will be evaluated using a comprehensive approach which includes measures of screening (# screened/mo), recruitment (# enrolled/mo), randomization (% eligible who enroll), and retention (% completing study). Acceptability will be assessed by a program satisfaction questionnaire at each assessment time point. Intervention engagement will be measured by the number of website logins, video lessons viewed, homework assignments completed, frequency of exercise planning, number of exercise days, and total exercise minutes.
- **Primary aim 2:** Compare treatment groups on 12- and 24-week changes in PA (steps, MVPA, bouts MVPA). We will stratify patients whether or not they are on maintenance/continuous treatments or not.
- **Secondary aim:** Compare treatment groups on changes in sleep, weight, and other questionnaire measures (e.g., fatigue, distress, anxiety, depression, health-related quality of life, fear of recurrence) at 12 and 24 weeks.

RESEARCH PLAN

Study Overview and Randomization. 50 participants will be randomized in equal numbers (permuted block structure, matched by biological sex and cancer type) at baseline to receive the 12-week Energize! Exercise Program (EEP) or to a standard of care control condition (CON). Assessments of PA, fatigue, sleep, distress, anxiety, depression, weight, health-related quality of life, and fear of cancer recurrence will occur at baseline, 12 weeks (post-intervention), and 24 weeks (following 12-week no-contact follow-up period). Following the 24-week assessment, participants randomized to CON will have the opportunity to participate in the EEP, if they desire, and complete an additional assessment at 36 weeks (upon completion of the EEP). Participants randomized to EEP will be provided with CON newsletters following the 24-week assessment.

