Recruitment & Enrollment. Participants will be primarily recruited via multiple avenues within the Lifespan Cancer Institute (LCI), the Miriam Primary Care Clinic, and the Oncology, Wellness, Lifestyle and Survivorship (OWLS) clinic. We will work with our LCI Patient Navigators and Advanced Care practitioners who work closely with oncology and radiation oncology and will help to identify patients who will be eligible. Clinical research assistants may also access healthcare records prior to patient visits to identify individuals who meet our inclusion criteria related to age, BMI, and duration of time following cancer treatment. If eligible based on that information, they may send them a message informing them about the study via the patient portal, the standard of care mechanism of contact, or ask patients about their physical activity levels at visits or via phone. Research assistants will either direct individuals to the online screener or help patients complete the online screener for the study. However, we may also work with other physician groups, post flyers, and advertise on various social media platforms (e.g., Facebook, Instagram, Twitter) to help spread the word about our research study. All interested individuals will complete an online screener to determine initial eligibility. If eligible, a research staff member will conduct a follow-up phone screen to confirm eligibility and schedule an orientation session where the study will be explained in detail and informed consent will be obtained. All participants will also be required to get physician clearance (see attached MD consent form) prior to randomization.

Participants. Individuals must have a confirmed cancer diagnosis and have either completed all cancer-directed treatment in the past 12 months or be on a maintenance/continuous treatment regimen. Individuals must also be 18-70 years of age, have a BMI between 18.5 and 45, have daily Internet access, free of any medical condition for which PA is contraindicated, and inactive, defined as engaging in <60 min/week of moderate-intensity PA over the past 3 months. Participants must also be English speaking, as the Internet program is currently in English. These broad inclusion criteria were selected to enhance generalizability of study findings and to provide us with preliminary data on the effectiveness of this program across cancer types.

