STATISICAL ANALYSIS PLAN:

Be-Active Study – Increasing Physical Activity for Cancer Survivors

NCT05376293

Analyses conducted 10/1/2024

The statistical analyses for this study were conducted using mixed-effects models to evaluate the impact of the program on various physical activity and psychological outcomes. The primary outcomes analyzed included self-reported moderate-to-vigorous physical activity (MVPA), total MVPA, and bouted MVPA over time.

For each outcome, mixed-effects models were employed, incorporating random intercepts for participants to account for the repeated measures design of the study. These models included fixed effects for time points, treatment arms, and their interaction, as well as baseline values of each outcome to control for initial differences across groups. Additional covariates such as age, BMI, weight, sex, education, racial/ethnic minority status, maintenance therapy, days since treatment completion, and daily wear time (for accelerometer-based outcomes) were also included. The primary interest was in the interaction between treatment arms and time points, which was used to evaluate whether changes in physical activity differed between the two groups (Energize! and Newsletter) at each time point (baseline, 3 months, and 6 months).

Post hoc pairwise comparisons of estimated marginal means (EMMs) were conducted to assess changes from baseline to 3 months and baseline to 6 months within each randomization group. Bonferroni corrections were applied to adjust for multiple comparisons.

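### Does adjusting for days since treatment completion remove participants on maintenance treatment from the physical activity models?

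*SAP*

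**What the plan says.** The second paragraph of the SAP sets out one model form for all outcomes: "For each outcome, mixed-effects models were employed, incorporating random intercepts for participants". The fixed effects are time, arm, their interaction and the baseline value of the outcome. Further covariates follow, ending with: "maintenance therapy, days since treatment completion, and daily wear time (for accelerometer-based outcomes) were also included". The list is introduced by way of example, so it need not be the exact set used in every model. The SAP does not define the days variable, assign it a value for people still on treatment, or give a rule for missing covariates.

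Under Research Plan, Participants, the protocol requires that people "have either completed all cancer-directed treatment in the past 12 months or be on a maintenance/continuous treatment regimen". Primary aim 2 adds: "We will stratify patients whether or not they are on maintenance/continuous treatments or not". The Background describes the study as contributing "by including those off all cancer treatment and those stable on continuous anticancer therapy", and notes that "there is a lack of evidence to inform whether these benefits extend to those survivors on extended treatments".

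**The concern.** Eligibility has two routes, and the second is being on treatment now. Read literally, a person who enters by that route has not completed treatment, so the number of days since completion has no obvious value. Mixed-model software usually drops any row with a missing covariate. If the field were blank for the on-treatment group, that whole group would be lost from every model carrying the term, and the loss would not be a random subset.

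The aim 2 estimates would then describe only people off treatment. Precision would fall in a trial of 50, and the planned stratification by maintenance status could not be delivered. Because the cut would be made on a baseline characteristic, the remaining comparison would still be a randomised one. The cost would be in population and precision rather than bias between arms. Aim 1 (feasibility, acceptability and engagement) does not use these models and is untouched.

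**Working it through.** **Inputs.** Fifty participants randomised in equal numbers (protocol, Study Overview and Randomization). The share on maintenance treatment is not stated, so 10%, 30%, 50% and 70% are assumed. Neither document gives a power calculation, a standard deviation or an expected number analysed, so there is no planned figure to reproduce.

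**Step 1: the size of the loss, if it occurred.** With n people left in equal arms and an unadjusted two-sample approximation:

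- SE factor = sqrt(50/n)
- 95% CI half-width, in SD units = t(0.975, n−2) × sqrt(4/n)

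| Assumed share | n left | SE factor | Half-width (SD) |
|---|---|---|---|
| 0% | 50 | 1.00 | 0.57 |
| 10% | 45 | 1.05 | 0.60 |
| 30% | 35 | 1.20 | 0.69 |
| 50% | 25 | 1.41 | 0.83 |
| 70% | 15 | 1.83 | 1.12 |

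Simulating a baseline-adjusted random-intercept model (100 data sets per share) gave similar median SE ratios: 1.05, 1.20, 1.43 and 1.86 for arm, and 1.06, 1.21, 1.41 and 1.78 for arm-by-time.

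**Step 2: is deletion compatible with what the SAP reports?** Let M be the maintenance indicator. If everyone with M = 1 is deleted, M is zero for all who remain and has no estimable coefficient. In a simulated data set with 15 of 50 on maintenance and the days value missing for them, 35 people (70 of 100 rows) remained and the fit stopped with a singular-matrix error. In a second, with 20 of 50 on maintenance, 30 people remained and the design matrix had rank 6 for 7 columns. The SAP, written in the past tense, reports both the maintenance term and the days term as included. That fits a model in which the on-treatment group was present.

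**Step 3: does the choice of coding matter?** Suppose on-treatment people are given a constant c, so that the covariate is D = (1−M) × days + c × M. With slope b for D and coefficient g for M:

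b × D + g × M = b × (1−M) × days + (g + b × c) × M

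Changing c is absorbed entirely by the maintenance coefficient. The arm effect, the arm-by-time effect and the days slope do not move. The first simulated data set shows this:

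| Constant used (days) | Arm (SE) | Arm-by-time (SE) | Maintenance coefficient |
|---|---|---|---|
| 0 | 0.668 (0.225) | −0.285 (0.284) | 0.669 |
| 365 | 0.668 (0.225) | −0.285 (0.284) | −0.073 |
| 999 | 0.668 (0.225) | −0.285 (0.284) | −1.362 |

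The shifts agree with the algebra: (0.669 + 0.073)/365 = 0.00203 and (0.669 + 1.362)/999 = 0.00203, the same slope. In the second data set, filling with 0 or with the off-treatment mean gave arm 0.8188 and arm-by-time 0.0269 both times. Only the maintenance coefficient changed (−0.3104 against 0.1245).

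**Step 4: the other reading.** The SAP's variable refers to treatment completion, whereas the eligibility criterion refers to completing all cancer-directed treatment. For some people on maintenance, the clock could run from the end of an earlier treatment phase. They would then have real values and no row would be lost. The invariance in Step 3 covers constant fills only, but on this reading no fill is needed.

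**The case for a change.** The strongest reply is that the omission is certain, whatever was done in practice. The affected group is one the protocol names as a reason for the study, and a single sentence would remove the doubt. Some packages drop an inestimable column with no more than a note, so reporting a term as included does not prove that its coefficient was obtained. If days since an earlier phase were used for some people and days since final treatment for others, two different clocks would share one slope.

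Much of this stands as a remark on completeness. The definition is missing, and the SAP's wording is evidence rather than proof. It does not make a case for changing the analysis. The harm needs two conditions that the documents do not show: a missing value, and deletion of the rows that carry it. Mixed clocks would affect the meaning of a nuisance coefficient more than the randomised arm comparison. Prescribing a particular coding now would also be premature: if real values exist for on-treatment participants, overwriting them with a constant would discard information. Numbers analysed by arm and treatment status belong in the results report.

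**Conclusion.** No change to the plan follows. The SAP leaves one covariate undefined for one eligible group, and the analysts had to resolve that before the model could be fitted. The SAP already lists the right pair of terms: with a maintenance indicator alongside the days variable, any constant for on-treatment participants leaves the arm and arm-by-time estimates unchanged, so the effect on the aim 2 comparison is nil.

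The SE factors of 1.05 to 1.83 describe a scenario in which the group was deleted, under maintenance shares that are assumed. They do not measure a defect shown in this SAP. The conclusion rests on taking the SAP at its word that both terms were fitted, and on the on-treatment group having either a constant or real values for days. It would change only if the reported numbers analysed showed that people on maintenance had been dropped.
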